To measure the energy expenditure using indirect calorimetry in mechanically ventilated children admitted to the intensive care unit before, during and after fever.

HYPOTHESIS

Null hypothesis: Fever will be associated with <10% difference of baseline energy expenditure per 1°C change in temperature in critically-ill children ventilated on the intensive care unit

Alternative hypothesis: Fever will be associated with a >10% difference of baseline energy expenditure per 1°C change in temperature

STUDY DESIGN

Prospective observational cohort study

STUDY POPULATION

Children admitted to the paediatric intensive care unit at Great Ormond Street Hospital with suspected infection, following trauma or major surgery, who are likely to develop a fever.

ELIGIBILITY CRITERIA

Inclusion criteria:

- Children >10kg (The MedGraphic Ultima CCM calorimeter has been used safely in children as low as 10kg)
- Children with suspected infection, following trauma, or post-major surgery

Exclusion criteria:

- Children post brain injury
- Children with refractory status epilepticus
- Children post cardiac arrest
- Children post cardiac bypass
- Children with cardiac arrhythmias
- Children not invasively ventilated
- Children with a greater than 5% leak around their endotracheal tube
- Children with a fraction of inspired oxygen (FiO_2)>0.60
- Children above 16 years of age

STUDY OUTCOMES

Primary outcome: Change in energy expenditure per degree Centigrade change in temperature

Secondary outcome: Change in oxygen extraction ratio (ratio of oxygen consumption to oxygen delivery) per degree Centigrade change in temperature using oxygen delivery data from the Lidco Rapid (LIDCO Ltd, UK) cardiac output monitor if in place.

STUDY PROCEDURES

Screening and Recruitment

- All patients will be screened each morning (Mon-Fri) by the PI for weight, ventilation status and likelihood of developing a fever (The PI is part of the wider clinical team)
- The PI will ask the clinical team on call if calorimetry is suitable for the identified patient/s
- If the clinical team feel this is appropriate, the PI will ask consent of the parents to undertake indirect calorimetry

Study procedure

1. Once consented, calorimetric measurement will be undertaken using the MedGraphic Ultima CCX, Minnesota, USA). This will be done in the following steps:
 - a. Assess the patient for stability:

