During measurement we will monitor the child's respiratory rate, oxygen saturation levels and end tidal CO₂. If any of these values change significantly, as judged by the bedside nurse or the PI, calorimetry will be discontinued.

Data collection

Data will be collected for

- Demographic data (ID, weight, height, age, sex, diagnosis)
- Inspired and expired O₂ and CO₂; VO₂ and VCO₂; Respiratory Quotient; Energy expenditure (as measured and displayed by the MedGraphics Ultima CCM calorimeter)
- Physiological variables (heart rate, blood pressure)
- IF CARDIAC OUTPUT MONITOR IN PLACE: stroke volume and cardiac index (as measured by Lidco Rapid, LIDCO Ltd, UK) and latest haemoglobin
- Inotrope infusion doses
- COMFORT or sedation score as recorded
- Paralysis (yes/no)
- Temperature
- Nutritional intake in last 24 hours or since admission

Data apart from demographic data will be collected at the start of each recording and hourly if continuous recording

If cardiac monitoring is in place, continuous data (as recorded by the Lidco Rapid) will be used to calculate oxygen delivery.

STATISTICAL ANALYSIS

Sample size: Not enough data exists to ascertain the standard deviation of energy expenditure using the Medgraphics Ultima CCM calorimeter in critically ill children over the time period to be measured. However a standard deviation of 10% has been observed in critically ill children by groups who have measured energy expenditure in large numbers of children (personal communication from Dr [name], Imperial College, London). Based on this, for a 10% effect size, with a one-tailed α of 0.05 and (1- β) of 0.8, a sample size of 10 children would be needed, provided a 1°C of temperature is seen. An analysis of temperature change following over 5000 doses of paracetamol in febrile children suggested a mean reduction of temperature by 0.7°C. Based on this therefore we will need $10 \times 1/0.7 = 15$ patients

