However it is likely that our sample will have several confounders which will need to be taken into account by multi-variable analysis. Therefore we will aim to recruit at least 15 children with measurements with and without fever (ideally before-during and after fever), but will try and recruit as many children as possible over the 12 month study period. Approximately 300 patients admitted to PICU at Great Ormond Street Hospital per year are above 10kg. Of these, approximately 75-100 patients are electively admitted, 30 post-major surgery (mostly spinal surgery). 30% of children post spinal surgery develop a fever in the first 24 hours. In addition the remaining 200 children are admitted as an emergency. 80% of children admitted as an emergency are treated for a suspected infection, the remainder post trauma. Again 30-50% of children admitted with an infection or trauma develop a fever within the first 24 hours. Therefore each year approximately 75-80 patients will be >10kg, ventilated, and will develop a fever within the first 24 hours of admission, with a proportion developing fever later on in admission (e.g. from nosocomial infections).

Statistical analysis: Uni-variable analysis using paired t-tests will be undertaken by comparing the energy expenditure with and without fever, divided by the change in temperature. Multi-variable analysis using a multi-level regression model will be used using

- Change in energy expenditure as the outcome variable
- Patient ID as the random effect variable
- Change in temperature, COMFORT score, vasoactive inotrope score, heart rate, blood pressure, and paralysis as a binary variable as fixed effect variables

If cardiac output monitoring is in place, then the oxygen extraction can be calculated as VO_2/DO_2 , where,

$DO_2 = \{cardiac\ index \times ((oxygen\ saturation\ of\ haemoglobin \times haemoglobin\ concentration) + 0.0031 \times partial\ pressure\ of\ oxygen)\}$

and VO_2 is measured from the calorimeter

ETHICAL CONSIDERATIONS

The study will be conducted in accordance to Good Clinical Practice principles and the principles of the Declaration of Helsinki.

Informed consent will be sought from parents/guardians with parental responsibility prior to measurement. Consent forms will be stored in the Great Ormond Street Critical Care Research Office securely.

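### The sample size is multiplied by 1/0.7 where the smaller expected effect calls for an inverse-square adjustment, so the 15 is not validly derived and its power is not established

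*Combined protocol and SAP*

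**What the plan says.** The Sample size paragraph under STATISTICAL ANALYSIS begins with a caveat about this calorimeter and population: "Not enough data exists to ascertain the standard deviation of energy expenditure". It then adopts a value from a personal communication, saying that "a standard deviation of 10% has been observed in critically ill children by groups who have measured energy expenditure". It does not say whether this is the SD of single readings or of the change within a child.

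For a 10% effect, one-tailed alpha of 0.05 and 80% power, it states "a sample size of 10 children would be needed, provided a 1°C of temperature is seen". It then cites an analysis of paracetamol doses that "suggested a mean reduction of temperature by 0.7°C", and finishes with "Based on this therefore we will need $10 \times 1/0.7 = 15$ patients".

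The next paragraph sets the target at "at least 15 children with measurements with and without fever", with as many more as can be recruited in 12 months. The Statistical analysis paragraph plans paired t-tests "comparing the energy expenditure with and without fever, divided by the change in temperature" and does not give their sidedness. The null in the HYPOTHESIS section is "Fever will be associated with <10% difference of baseline energy expenditure per 1°C change in temperature".

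**The concern.** The 0.7 is a mean temperature change. At 10% per 1°C it shrinks the change to be detected from 10% to 7%. Sample size for a mean change depends on (SD/effect)², so a smaller effect enters squared. Dividing once by 0.7 would suit a study in which 70% of enrolled children were evaluable, but the protocol does not use the figure in that sense.

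What is at stake is the power claimed for the 15-child minimum. The text implies 80%. Whether 15 children deliver that depends on an SD the protocol does not define, and the linear step hides this dependence.

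**Working it through.** **Inputs from the protocol.** Effect 10% of baseline at 1°C; SD 10%; one-tailed alpha 0.05; power 80%; base of 10 children; mean temperature change 0.7°C; paired t-test.

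**The protocol's own figure.** 10 × 1/0.7 = 14.29, rounded up to 15. The arithmetic is right; the formula is not.

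**The scaling.** The expected change at 0.7°C is 10% × 0.7 = 7%. At a fixed SD, n is proportional to (SD/effect)², so the factor is (10/7)² = 1/0.49 = 2.04, not 1.43. Dividing each child's change by the temperature change does not alter this. At a uniform 0.7°C the mean ratio is 7/0.7 = 10% and its SD is SD/0.7, so effect divided by SD is still 7/SD.

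**Direct calculation.** With n children, mean change δ and SD of change s, the paired t-test has power P(T > t_crit), where T is non-central t with n − 1 degrees of freedom and non-centrality (δ/s)√n, and the null is zero change. The minimum n is the smallest that reaches 80%.

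| SD of change | Test | Minimum n at 10% | Minimum n at 7% | Power of 15 at 7% |
|---|---|---|---|---|
| 10% | one-tailed | 8 | 15 | 82.4% |
| 11.0–11.7% | one-tailed | 10 | 17–19 | 75.7–71.0% |
| 14.1% | one-tailed | 14 | 27 | 57.1% |
| 10% | two-tailed | 10 | 19 | 71.3% |

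- Row 1 takes the stated 10% as the SD of within-child change. Power is 81.5% with 8 at a 10% change (75.4% with 7), and 82.4% with 15 at a 7% change (79.8% with 14).
- Row 2 takes the protocol's 10 as correct and finds the SDs of change for which 10 is the one-tailed minimum.
- Row 3 takes the 10% as the SD of single readings with an assumed within-child correlation of 0, so the SD of change is 10 × √2 = 14.1%. A positive correlation would reduce it: at an assumed 0.5 it is 10 × √(2 × 0.5) = 10%, which is row 1.
- Row 4 shows that 10 is exactly the two-tailed answer at an SD of change of 10% (80.3% power; 74.8% with 9).

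**Do the 10 and the 15 share an SD?** As one-tailed minimum sample sizes they do not: 10 at a 10% change needs an SD of change of about 11.0–11.7%, and 15 at a 7% change needs about 10.0–10.4%.

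**The case against.** The strongest reply is that 15 may be the right number. If the 10% is the SD of within-child change, the correct one-tailed calculation at 7% gives exactly 15. The protocol also treats 15 as a floor, intends to recruit beyond it, and expects about 75–80 febrile, ventilated children above 10 kg a year. All of this stands, and it limits the consequence. It does not rescue the derivation: on that reading the 10 is not the one-tailed answer, and the 15 is reached only because two departures happen to offset each other.

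Linear scaling could also be defended if the variance of the change in energy expenditure were proportional to the temperature change. Nothing in the protocol says so.

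A reader might infer three stronger things that the documents do not support.

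- *That 21 children are needed.* Simple scaling of the 10 gives 10/0.49 = 20.4, but this carries an already rounded number through a large-sample formula. With the paired t-test that the protocol plans, the range is 17–19.
- *That 10 and 15 cannot both have at least 80% power.* They conflict only as minimum sample sizes. At an SD of change of 10%, 10 children give 90% power at a 10% change and 15 give 82% at a 7% change.
- *That 15 has been shown to be too few.* This depends on the undefined SD and on the sidedness.

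**Conclusion.** The step from 10 to 15 is wrong as written, and the 80% power it implies for 15 children is not established. If the base of 10 is a correct one-tailed minimum, 17–19 children are needed at 0.7°C and 15 give 71–76%. If the SD of within-child change is 10%, 15 is adequate one-tailed at 82%, while the same inputs two-tailed give 71% and call for 19. If 10% is the SD of single readings and the correlation is 0 (assumed), 15 give 57%.

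These figures assume that every child changes by 0.7°C and that the true effect is 10% per 1°C, tested against zero change. They do not carry over to the null in the HYPOTHESIS section, because a true effect of 10% per 1°C lies on that null's boundary. For scale, with an SD of change of 10% the SD of the per-degree change is 10/0.7 = 14.3%. Fifteen children reach 80% one-tailed power at a standardised difference of 0.675, so the true effect would have to be about 10 + 0.675 × 14.3 = 19.6% per 1°C. That mismatch is a separate matter and does not enlarge the scaling error.

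**What to change.** Rewrite the sample-size derivation as follows.

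- Replace the multiplication by 1/0.7 with one direct paired-t calculation at a 7% change (10% per 1°C × 0.7°C).
- State that the 10% is taken as the SD of within-child change, or give the SD of change that is assumed instead.
- Use one sidedness in both the Sample size and Statistical analysis paragraphs.
- Restate the power of 15 children under those assumptions: 82% one-tailed at an SD of change of 10%, and 57% if the 10% is the SD of single readings with an assumed correlation of 0.
- State that this power is for a null of zero change and does not apply to the null of less than 10% per 1°C in the HYPOTHESIS section.

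The cost is one rewritten paragraph, a clause giving the sidedness of the t-test, and a stated power that may look less favourable. The minimum of 15 need not change because of the scaling error alone.

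### The hypothesis is set at 10% of baseline energy expenditure per 1°C, but the outcome and tests never divide by baseline and name no 10% null value

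*Combined protocol and SAP*

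**What the plan says.** Under HYPOTHESIS, the null is "Fever will be associated with <10% difference of baseline energy expenditure per 1°C change in temperature" and the alternative is "Fever will be associated with a >10% difference of baseline energy expenditure per 1°C change in temperature". OUTCOMES AND SIGNIFICANCE ties the study's conclusion to these two statements. If the null holds, treating fever can be questioned; if the alternative holds, a randomised trial is called for.

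Under STATISTICAL ANALYSIS, the sample size paragraph also works in percent. It says that "a standard deviation of 10% has been observed in critically ill children" and plans "for a 10% effect size, with a one-tailed α of 0.05 and (1- β) of 0.8". It does not say what the 10% is a percentage of.

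The percent is absent from the outcome and the analysis:

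- STUDY OUTCOMES: "Primary outcome: Change in energy expenditure per degree Centigrade change in temperature".
- Data collection: "Energy expenditure (as measured and displayed by the MedGraphics Ultima CCM calorimeter", that is, the value the device shows.
- Statistical analysis, t-test: "comparing the energy expenditure with and without fever, divided by the change in temperature". The only divisor named is temperature.
- Statistical analysis, multilevel model: the outcome is the change in EE. Neither baseline EE nor body weight is among the listed fixed effects.

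No section divides by baseline EE, takes logs, indexes EE to weight, or gives 10% as the value to test against. The INTRODUCTION likewise describes the target only as an average increase in EE per 1°C.

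**The concern.** Two things are needed to test the stated hypothesis: an outcome in percent of baseline per °C, and a null value of 10%. The analysis text supplies neither.

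On scale, a slope in energy units per °C has no threshold in the plan to be judged against. No single energy value can stand in for 10%, because eligibility runs from just over 10 kg up to 16 years of age and baseline EE will differ widely across that range.

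On the null value, a paired t-test compares with zero unless told otherwise. A significant result would then show that EE rises with temperature, not that it rises by more than 10% per °C. The two conclusions lead to different next steps in the plan, so a real but small effect could be read as support for the alternative hypothesis.

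**Working it through.** **1. The plan's own sample size.** Inputs from the sample size paragraph: effect 10%, SD 10%, one-tailed α 0.05, power 0.80, stated N of 10 for a 1°C change, then 15 for an expected change of 0.7°C.

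- Paired t-test against zero, standardised effect 10/10 = 1.0, noncentral t: 8 children one-sided. The two-sided version gives 10 (power 80.3%).
- Scaling: 10 × 1/0.7 = 14.3, rounded up to 15. A direct one-sided calculation for a 7% effect with SD 10% also gives 15 (power 82.4%).

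So the stated figures are reproduced closely, and they are figures for a test against zero. The effect planned for, 10% per °C, is the boundary of the stated null.

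**2. Why one energy value cannot represent 10%.** The documents give no baseline EE, so assume 500, 1000 and 1800 kcal/day for children of different size.

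| Assumed baseline (kcal/day) | 10% per °C equals (kcal/day per °C) | A slope of 100 kcal/day per °C equals |
|---|---|---|
| 500 | 0.10 × 500 = 50 | 100/500 = 20% |
| 1000 | 0.10 × 1000 = 100 | 100/1000 = 10% |
| 1800 | 0.10 × 1800 = 180 | 100/1800 = 5.6% |

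**3. What each test does at n = 15.** Assumptions: percent slopes normal with SD 10 points per °C, independent of body size; baselines uniform from 500 to 1800 kcal/day; one-sided 0.05. On the percent scale the rejection rate follows from the noncentral t with standardised effect (true slope − null value)/10 and 14 degrees of freedom. The energy-unit column comes from simulation.

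| True slope (% per °C) | Energy units, null zero | Percent, null zero | Percent, null 10% |
|---|---|---|---|
| 5 | 55% | 58% | 0% (under 0.1%) |
| 8 | 88% | 90% | 0.9% |
| 10 | 97% | 98% | 5% |

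The first two rows lie inside the stated null and the third is on its boundary. Moving from energy units to percent while keeping zero as the null changes almost nothing. Moving the null value to 10% changes the result entirely.

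**4. What the scale alone costs.** Under the same assumptions at a true 10% per °C, mean energy change divided by mean baseline averages 10.0%, so there is no bias. Its standard error is about 2.70 points, against 10/√15 = 2.58 for the mean of the children's percent slopes. The ratio 2.70/2.58 = 1.05 is a loss of about 5%.

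**5. Power once 10% is the null.** With the same assumed SD, one-sided 0.05 and 80% power:

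| Assumed true slope (% per °C) | Standardised effect | Children needed | Power at n = 15 |
|---|---|---|---|
| 20 | (20 − 10)/10 = 1.0 | 8 | 98% |
| 15 | (15 − 10)/10 = 0.5 | 27 | 58% |
| 12 | (12 − 10)/10 = 0.2 | 156 | 18% |

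**The case against.** The best defence is that percent was meant throughout. The hypotheses stand just above the primary outcome and give the scale explicitly, the sample size is in percent, and the documents never use the word absolute or give a unit for the outcome. Each child's EE with and without fever is recorded, so percent change is one division away.

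Much of this stands. A reader might infer that the plan has committed to an energy-unit scale, or that its data cannot answer the question. The documents support neither: the scale is unstated, and the data are sufficient. But the analysis text names temperature as its only divisor, and intent on scale would still leave the null value unstated. Leaving both open allows them to be settled after the data are seen.

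A reader might also infer that large children will pull the answer across 10%. Such a case can be built: if half the children have a baseline of 500 kcal/day and respond by 14%, and half have 1500 and respond by 6%, the mean response is 10% but the energy-unit result is (0.14 × 500 + 0.06 × 1500)/2000 = 8.0% of mean baseline; with the responses swapped it is 12.0%. This needs percent response to vary with body size, on which the documents are silent. It is not an expected effect.

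Nor should the high rejection rates be put down to scale. The comparison above shows nearly the same rates on the percent scale against zero.

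**Conclusion.** The point holds in this form: the analysis, followed as written, does not test the hypothesis on which the study's conclusion depends. The outcome lacks the division by baseline, and the test lacks the 10% null value. The missing null value does most of the harm. At 15 children and an assumed slope SD of 10 points per °C, a test against zero rejects in more than half of studies at a true 5% per °C and in roughly nine in ten at 8%, where a test against 10% rejects in under 1%. The scale by itself is a smaller matter: about 5% of precision under the assumed baselines, and bias only if percent response depends on size.

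The arithmetic behind 10 and 15 children is not the fault found here. Those numbers simply answer the question of any rise, not of a rise above 10%. The rejection rates rest on the assumed slope SD, and those for energy units and the precision figure also on the assumed baseline range. The mismatch itself rests only on the text.

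**What to change.** - Define the primary outcome for each child as 100 × (EE with fever − EE without fever) / afebrile EE / temperature change, in percent per °C.
- State which afebrile reading is the baseline when there are readings both before and after fever. State it also for children febrile at screening, who enter the study procedure at step 2 and have no pre-fever reading.
- Test this outcome one-sided against 10% per °C, or compare its confidence interval with 10%.
- Use the same percent scale for the outcome of the multilevel model, so that its temperature coefficient can be set against 10%.
- Log EE, with the threshold at ln 1.10 ≈ 0.095 per °C, can be a sensitivity analysis.

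The cost is wording in STUDY OUTCOMES and STATISTICAL ANALYSIS; every variable needed is already collected. The sample size text should add that 15 was derived for a test against zero, and should show the power against 10% for a range of true slopes, so that a non-significant result is not read as proof of the null.

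### The multi-level model uses change in energy expenditure as its outcome and adds a patient random effect; fitted in the usual way, its temperature coefficient can be much less precise than that from a model of the readings themselves

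*Combined protocol and SAP*

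**What the plan says.** The Study outcomes section gives "Primary outcome: Change in energy expenditure per degree Centigrade change in temperature". The Statistical analysis section then plans two analyses.

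- **Unadjusted:** paired t-tests of energy expenditure in and out of fever, with the difference divided by the temperature change.
- **Adjusted:** a multi-level regression with "Change in energy expenditure as the outcome variable" and "Patient ID as the random effect variable". The fixed effects are change in temperature, COMFORT score, inotrope score, heart rate, blood pressure and paralysis. The plan expects several confounders and relies on this model to deal with them.

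The text does not say how a change is formed or signed, how many changes a child contributes, or whether a fixed intercept is kept. It does not say which estimate stands for the primary outcome, and it gives no SD for the temperature change.

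**The concern.** A patient random effect is useful when the rows are raw readings, because it absorbs stable differences between children. Here the outcome is already a within-child difference, so those differences have gone. Two consequences follow from a standard fit.

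- With a single change per child, the patient effect and the residual are the same quantity and cannot be separated.
- A standard fit has an intercept. If every change is fever minus no fever, every temperature change is positive and the changes may be similar in size. The slope then rests only on the spread of temperature changes between children. It makes no use of the fact that no temperature change should mean no energy change, which the unadjusted ratio does use.

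The Outcomes and significance section says that a true null would call the treatment of fever into question. A wide interval from the adjusted model, read as no temperature effect, would lean that way for reasons unrelated to physiology.

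**Working it through.** **1. The plan's own figure.** Inputs from the sample size paragraph: "with a one-tailed α of 0.05"; power "of 0.8, a sample size of 10 children would be needed"; "for a 10% effect size"; "a standard deviation of 10% has been observed in critically ill children". The standardised effect is 10/10 = 1. A paired t-test with 80% power needs 8 children one-sided and 10 two-sided, so 10 is reached. The paracetamol data "suggested a mean reduction of temperature by 0.7°C", and 10/0.7 = 14.3, rounded up to 15. The plan states no precision for the multi-level coefficient, so the rest is derived.

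**2. Formulas, one same-sign change per child, no covariates.** Let n = 15, σ = 10% (taken here as the SD of a change; the plan does not say which SD it is), m = 0.7°C the mean temperature change and s its SD between children.

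- Slope with a free intercept: SE ≈ σ/(√n · s)
- Slope through the origin: SE ≈ σ/√(n(m² + s²))
- Ratio: √(1 + m²/s²), which does not depend on σ or n

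A level model reaches the second SE. With two readings per child, each with error variance σ²/2, the within-child temperature sum of squares is Σ(ΔT²)/2. The slope variance is then (σ²/2)/(Σ(ΔT²)/2) = σ²/Σ(ΔT²).

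**3. Numbers.** The values of s are assumptions; SEs are in % per °C.

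| s (°C) | SE, free intercept | SE, through origin or level | Ratio |
|---|---|---|---|
| 0.2 | 12.9 | 3.5 | 3.6 |
| 0.25 | 10.3 | 3.5 | 3.0 |
| 0.3 | 8.6 | 3.4 | 2.5 |
| 0.5 | 5.2 | 3.0 | 1.7 |
| 0.7 | 3.7 | 2.6 | 1.4 |

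Simulation with temperature changes floored at 0.2°C, which narrows the spread, gives 14.6 against 3.5 at s = 0.2 (ratio 4.2) and 5.1 against 2.8 at s = 0.7 (ratio 1.8). Together the range is roughly 1.4 to 4.

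**4. What this means for a test.** For a true cost of 10% per °C, the one-tailed 5% power with and without an intercept is:

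- s = 0.2: 18% and 84%
- s = 0.3: 26% and 86%
- s = 0.5: 45% and 92%
- s = 0.7: 62% and 95%

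These are tests against zero without covariates. They are not the power of the protocol's hypothesis, whose boundary is 10% per °C.

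**5. Bias.** With energy change set to 10 × temperature change and s = 0.25, the free-intercept slope averages 10.1 and the intercept −0.1, so there is no bias. With a fixed fever cost of 7% whatever the rise, the slope averages −0.2 and the intercept 7.1, while the through-origin slope averages 9.0.

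**6. Other data layouts.**

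- Several febrile rows per child against one shared reference (between-child SD 0.3, within-child SD 0.15): SE 6.6 against 2.9 with 2 rows, 5.1 against 2.5 with 4, and 3.9 against 2.3 with 8. The ratios are 2.3, 2.0 and 1.7.
- Within-child SD 0.3 and 8 rows: 2.3 against 1.8, ratio 1.3.
- A simulation of readings falling back to baseline: ratio about 1.2.
- One rise and one fall per child, entered with opposite signs: ratio 1.0.

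**7. Covariates.** With five covariates at raw levels (illustrative distributions, s = 0.3), the change model has an SE of about 13 with an intercept and 11.9 without. Heart rate alone raises the no-intercept SE to 9.5. The level model with five illustrative covariates stays at about 3.8.

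**The case against.** The strongest reply is that the worst case rests on choices the plan does not make. It specifies neither an intercept, nor one change per child, nor same-sign changes. The objective and the sample size text look for readings before, during and after fever, and the procedures allow continuous recording. A child already febrile at screening starts in fever, so the natural change there is a fall. Signed rises and falls would remove the loss, and repeated rows reduce it. This stands, and it is why the size is given as a range. It does not remove the point. The plan does not say that changes are signed in time order, and its wording for the paired comparison, energy expenditure with and without fever, reads more naturally as fever minus no fever.

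A reader might infer that the average fever effect disappears into the intercept, so that the slope is not the primary outcome at all. The documents do not support that. A slope of energy change on temperature change is a fair reading of the stated outcome, and under proportionality it is unbiased. Absorption needs a fixed fever cost whatever its height, which the documents nowhere assume.

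A reader might also fix the loss at about three times. That needs a temperature-change SD near 0.25°C, which the plan does not give, and one same-sign change per child.

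Finally, the unadjusted ratio analysis targets the outcome without an intercept, nothing says the adjusted coefficient alone decides the hypothesis, and 15 children is a minimum. All of this stands and lowers the severity.

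**Conclusion.** The point holds as a loss of precision and an unclear target in the adjusted analysis; bias is not shown. With 15 children and one same-sign change each, the SE of the temperature coefficient is roughly 1.4 to 4 times what the same readings could give, for an assumed temperature-change SD of 0.7 down to 0.2°C around the plan's mean of 0.7°C. The ratio was about 1.2 to 2.3 in the repeated-reading cases examined and near 1 with signed rises and falls. Only a fixed fever cost would make the slope average zero. With a single change per child, the patient effect cannot be estimated. The documents do not support the further inference that the study would wrongly accept its null, because the unadjusted analysis is unaffected and no decision rule rests on the adjusted coefficient alone. This should be fixed because a better model of the same data is available, and it kept its precision when covariates were added.

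**What to change.** Rewrite the multi-level specification as follows.

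- **Outcome:** energy expenditure at each reading, preferably on the log scale, otherwise as a percentage of the child's afebrile value. Include the afebrile readings as rows.
- **Temperature:** the value at that reading, as a fixed effect. If the percentage scale is used, measure temperature from the child's own afebrile value, because every child's reference row is then 100 and the random intercept cannot absorb differences in afebrile temperature.
- **Patient ID:** random intercept.
- **Covariates:** their values at the same reading.
- **Estimand:** state that the temperature coefficient is the adjusted estimate of the primary outcome.

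Do not rely on dropping the intercept from the change model, because uncentred covariates such as heart rate then act as an intercept. If changes are kept, say how they are formed and signed, enter the covariates as changes too, and omit the patient effect where each child has one change.

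The cost is a short edit to the analysis section, with no extra measurements or children.
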